#### Master Clinical Protocol 2018-10

#### 10.7 Data Collection

Subject data will be collected on CRFs and provided to the Sponsor. After subjects have provided informed consent, demographics, medical history, social history, and family history will be obtained. The clinical site will send a copy of available colonoscopy reports and applicable histopathology reports and/or other diagnostic information to the Sponsor. All reports that are provided to the Sponsor will be deidentified of all protected health information, prior to submission to the Sponsor.

#### 10.8 End of Study

Subjects will be considered completed from the study when they have provided a stool sample and have completed their colonoscopy procedure, OR at the point of subject withdrawal per Section 9.3.

Ensure all data is assessed, entered into the CRF and reporting on AEs/SAEs, UADEs, and/or Protocol Deviations has occurred, if necessary.

#### 10.9 Sample Retention

Retained samples comprise of residual stool samples. Retained subject samples will not be used other than to develop and evaluate the performance of biomarker assays to detect cancers. Retained samples will be de-identified of all protected health information, and clinical study data will only be associated by a subject identification number. Samples will be stored for no more than 20 years in Exact Sciences' or designee's on-site biorepository and will be used for developing and evaluating the performance of biomarker assays for cancer detection. Specimens de-accessioned from the biorepository will be destroyed under standard biohazardous material protocol and record of the removal and destruction will be maintained for 7 years by the Sponsor. Retained subject samples will not be used for any other purposes.

#### 10.10 Unusable Samples

Subjects who provide stool samples which are insufficient for testing may be asked to provide another stool sample if the subject has not yet begun bowel preparation for colonoscopy.

#### 11 ADVERSE EVENT REPORTING

#### 11.1 Definition of Adverse Events

An adverse event (AE) is any unfavorable or unintended sign, symptom, or disease temporally associated with the use of an investigational product or protocol-imposed intervention, regardless of attribution.

The liquid buffer/liquid preservative in the quantities provided is non-toxic.

An AE may be investigated as an Unanticipated Adverse Device Effect (UADE), if applicable.

Adverse events commonly associated with colonoscopy will not be collected. Such events include: Abdominal discomfort, bowel irregularity, bleeding, intestinal perforation, and adverse reaction to the sedation.

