#### 4 BACKGROUND / RATIONALE

#### 4.1 Background

The 2018 American Cancer Society colorectal cancer (CRC) screening guideline [1] now recommends initiating colorectal cancer (CRC) screening at age 45 in asymptomatic, average risk individuals. This change in a prominent national guideline was based on recent data [2] showing that the incidence of CRC in the 40-49 age group has increased with that of the 45-49-year-old group similar to that of 50-54-year-olds. There has been a 51% increase in the incidence of CRC from 1994 to 2014 and an 11% increase in mortality from 2005 to 2015 among individuals 55 years old and younger. Importantly, this change appears to be a birth cohort effect, likely starting for those born in the early 1950s who will carry this increased risk forward for their lifetimes. Compared to birth cohorts between 1890-1950 where the rate of CRC has been steadily declining, the rate in those generations born after 1950 has been steadily increasing. The ACS estimates that in 2014, over 7,073 cases of CRC were diagnosed in individuals aged 45 to 49 years with over 16,450 cases diagnosed in patients under 50.

Rising incidence of CRC in 40-49-year-olds compared to decreasing incidence in those 50 years of age and older (from Siegel R et al JNCI 2017 [2]).

Previously, a recommendation for starting at age 45 in average risk individuals was proposed by the 2009 American College of Gastroenterology guideline in African Americans [3] and reiterated in the 2017 U.S. Multi-Society Task Force CRC screening guideline [4]. The USMSTF includes members of the American Gastroenterological Association, the American College of Gastroenterology, and the American Society of Gastrointestinal Endoscopy. While the 2016 United States Preventive Services Task Force guideline did not recommend starting screening at age 45 [5] and continued to give its "A" rating to screening asymptomatic average risk individuals from ages 50-75, the data supporting a cohort effect generally showing increased risk in younger individuals were not available when the USPSTF reviewed the CRC screening evidence base prior to the 2016 guideline update.

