#### Master Clinical Protocol 2018-10

#### 7 STUDY DESIGN

This is a prospective, cross-sectional, multi-center study to confirm the specificity of the mt-sDNA test (Cologuard) in average risk individuals ages 45 to 49.

All subjects enrolled into the study will be provided a stool collection kit for the mt-sDNA test (Cologuard) and scheduled for a screening colonoscopy. Stool sample collection must occur prior to subjects initiating bowel preparation for the colonoscopy procedure. All subjects will undergo a screening colonoscopy within approximately 60 days of enrollment.

The results of the mt-sDNA test (Cologuard) will be compared with the results of the colonoscopy and with any corresponding diagnostic histopathology results from biopsies or excised tissues obtained for clinical purposes to confirm the performance estimates.

Stool samples collected by the subject for the mt-sDNA test (Cologuard) will be sent to Exact Sciences Laboratories and tested. Individuals conducting the mt-sDNA tests will be blinded to all subject clinical information, including colonoscopy results. Investigators, subjects, and endoscopists will be blinded to the mt-sDNA test (Cologuard) results, and the results of the tests will not be used for clinical management of study subjects.

All subjects enrolled in the study will also be offered the opportunity to provide a blood sample for biomarker evaluation and assay optimization (Protocol 2018-10B). Blood samples will be used for research on biomarkers from plasma and serum.

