#### 10.6 Colonoscopy and Histopathology

Every subject will undergo a screening colonoscopy after completing a mt-sDNA test (Cologuard) test. Colonoscopies should occur as soon as possible following informed consent and stool collection. Subjects who have poor bowel preparation and will not repeat the procedure or subjects who do not complete a colonoscopy should be withdrawn and may be replaced. Bowel preparation procedures and colonoscopy will be performed following the usual practice at each clinical site. Personnel performing the colonoscopy and producing the resulting report and the personnel performing the histopathological review of tissue will remain blinded to the results of the mt-sDNA test (Cologuard) result.

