#### 11.3 Serious Adverse Events

Serious adverse events are not expected for this study but will be reported to the Sponsor if they occur.

A serious adverse event (SAE) is any AE that results in one or more of the following outcomes.

- Death; Note: "Death" should not be reported as an SAE. The cause of death should be reported
  as the SAE. The only exception is "Sudden Death" when the cause is unknown.
- A life-threatening illness or injury;
- A permanent impairment of a body structure or a body function;
- Required in-patient hospitalization or prolongation of existing hospitalization;
- Necessitates medical or surgical intervention to prevent permanent impairment of a body structure or a body function; or
- Fetal distress, fetal death or a congenital abnormality or birth defect.

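### Serious complications of the study-required colonoscopy are reportable as SAEs but excluded from AE collection, so they could go unrecorded

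*Protocol*

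**What the plan says.** **What counts as an adverse event.** Protocol Section 11.1 covers unfavorable events "temporally associated with the use of an investigational product or protocol-imposed intervention, regardless of attribution".

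**What is left out.** The same section then says "Adverse events commonly associated with colonoscopy will not be collected" and lists the events meant: "Abdominal discomfort, bowel irregularity, bleeding, intestinal perforation, and adverse reaction to the sedation". Serious cases are not excepted. SAP Section 3.2 repeats both the definition and the exclusion.

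**When collection stops.** Section 11.2 limits recording to events linked to use of the stool test and ends it when the kit is returned. Footnote 3 of Appendix 2 likewise confines recording to stool collection.

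**What must be reported.** Section 11.3 treats an SAE as any AE with one of the listed outcomes, which include hospital admission and surgery to prevent permanent impairment. It adds: "Serious adverse events are not expected for this study but will be reported to the Sponsor if they occur". Section 11.5.1 requires notice to the sponsor within 24 hours of awareness, and at once for fatal or life-threatening events. Neither section mentions colonoscopy.

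**Status of the colonoscopy.** Section 7: "All subjects will undergo a screening colonoscopy within approximately 60 days of enrollment". Section 10.6: "Every subject will undergo a screening colonoscopy after completing a mt-sDNA test (Cologuard) test".

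**The concern.** The colonoscopy is the reference procedure of the study, and the protocol imposes it on everyone who enrolls. Its most important complications fall within the protocol's own AE definition and, if they lead to admission or surgery, within its SAE definition. The exclusion in Section 11.1 and the window in Section 11.2 say that the same events are not collected.

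A site coordinator who learns that a subject was admitted with a perforation would find two instructions in Section 11 and no statement of which prevails. One site could send an SAE form within 24 hours while another records nothing. SAP Section 3.2 promises a separate summary of SAEs. If that summary shows zero, a reader could not tell whether no serious event occurred or none was collected.

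**Working it through.** The point concerns consistency of the text and disputes no figure in the plan. The first step sets the rules side by side for one case: a perforation after the study colonoscopy that leads to hospital admission.

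| Question | Where | Answer |
|---|---|---|
| Was the procedure imposed by the protocol? | Protocol 7, 10.6 | Yes, for every subject |
| Does the AE definition cover the event? | Protocol 11.1, SAP 3.2 | Yes, whatever the cause |
| Is the outcome serious? | Protocol 11.3 | Yes (admission) |
| Must it be reported? | Protocol 11.3, 11.5.1 | Yes, within 24 hours of awareness |
| Is it to be collected? | Protocol 11.1, SAP 3.2 | No (perforation is named) |
| Is it inside the AE window? | Protocol 11.2, Appendix 2 footnote 3 | Normally no: stool is collected before bowel preparation, so the kit is usually back before the procedure |
| Is reporting checked afterwards? | Protocol 10.8 | Yes: SAE reporting is to be confirmed at end of study, which for completers follows the colonoscopy |

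Rows four and seven point one way, rows five and six the other. No separate SAE window is given.

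**Other routes.** The UADE definition in Section 11.4 is tied to the device. Colonoscopy reports go to the sponsor under Section 10.7 and might show an immediate complication, but they are not a defined safety collection and could miss a delayed one.

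**Scale.** The documents give no rate of serious colonoscopy complications, so the rates q below are assumptions. For the number of colonoscopies N, take 731 (the evaluable target in Section 12.3) and 914 (the enrollment target). The plan's own figure reproduces: 731 / 0.8 = 913.75, rounded up to 914.

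Expected events = N × q. Chance of at least one = 1 − (1 − q)^N.

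| Assumed q | Expected, N = 731 | Chance, N = 731 | Expected, N = 914 | Chance, N = 914 |
|---|---|---|---|---|
| 0.1 per 1,000 | 0.07 | 7.0% | 0.09 | 8.7% |
| 0.5 per 1,000 | 0.37 | 30.6% | 0.46 | 36.7% |
| 1 per 1,000 | 0.73 | 51.9% | 0.91 | 59.9% |
| 2 per 1,000 | 1.46 | 76.9% | 1.83 | 84.0% |

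For example, 1 − 0.999^914 = 0.599. Using the SAP's maximum enrollment of about 942 changes little: 9.0% at the lowest rate and 84.8% at the highest. The result is driven by the assumed rate.

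**The case against.** The strongest reply is that the narrow scope is deliberate. Section 11.2, the Appendix 2 schedule and its footnote 3 all limit AE recording to stool collection, SAP Section 3.2 repeats the exclusion, and the SAP defines the Safety Population by attempted use of the kit. A broad definition followed by a specific exclusion is ordinary drafting. Since an SAE is a kind of AE, the limits could be read as carrying through to Section 11.3. The study is about the specificity of a stool test, and no colonoscopy safety analysis is planned.

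Much of this stands. The exclusion is a choice, not a slip, and for non-serious expected events there is no reason to disturb it. It does not settle the serious cases. The exclusion itself calls these events adverse events, Section 11.3 makes any AE with a serious outcome an SAE, and neither Section 11.3 nor Section 11.5.1 says that the exclusion reaches that far. The protocol gives routine care as its reason for excluding surgical complications, but gives no reason for colonoscopy.

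A practical objection also stands: participation ends at the colonoscopy and no later contact is scheduled, so full capture of delayed bleeding or perforation would need a new follow-up step.

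Two stronger readings should be resisted:

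- A reader might infer that colonoscopy at this age lies outside standard of care, because Section 4.1 notes that the 2016 national "guideline did not recommend starting screening at age 45". The same section opens with a 2018 guideline that does recommend it, and Section 15.1.2 treats the colonoscopy results as standard of care. The conflict in Section 11 exists either way.
- A reader might infer from Section 15.1.1 that colonoscopy risk was not disclosed to subjects. That section deals with the stool test and kit, and the consent pages are not among the documents available here.

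**Conclusion.** The inconsistency is real and should be resolved. Protocol Sections 11.1 and 11.2, Appendix 2 footnote 3 and SAP Section 3.2 keep colonoscopy events out, while the AE definition and Sections 11.3 and 11.5.1 bring the serious ones in. A serious complication of a study-required procedure could go unrecorded, and zero reported SAEs would carry no clear meaning.

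The right strength is could, not would. A reader might infer that such events are certain to be lost, but Section 11.3 can be read as still requiring a report, and colonoscopy reports reach the sponsor.

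The effect is confined to safety reporting. The specificity endpoint, its 85.0% threshold and the sample size do not change. The probabilities (7-9% at 0.1 per 1,000, 77-84% at 2 per 1,000) rest wholly on assumed rates and show only that an event is plausible. The conflict in the text depends on no rate.

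**What to change.** Reconcile Protocol Sections 11.1, 11.2 and 11.3, Appendix 2 and SAP Section 3.2:

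- Keep the exclusion of non-serious expected colonoscopy events.
- State that the exclusion and the kit-return window do not override Sections 11.3 and 11.5.1. Any event that meets the Section 11.3 seriousness criteria, and that the site becomes aware of after the study colonoscopy, is reported as an SAE.
- State the end point of that SAE window, chosen by the sponsor.
- Make the rule depend on site awareness, so that no new visit or contact is needed.
- In SAP Section 3.2, say that the SAE summary includes these events.

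The cost is a wording change in both documents and probably a few more SAE forms. The limitation is that delayed events that never come to the site's attention may still be missed, and the safety summary should say so.

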#### Master Clinical Protocol 2018-10

Surgical intervention, such as, but not limited to, colectomy and sub-mucosal resection are part of routine patient care for subjects with CRC or AA; therefore, adverse events commonly associated with surgeries will not be collected. Such events include: Bleeding, blood clots in the legs (deep vein thrombosis) and lungs (pulmonary embolism); infection; injury to organs near the colon, such as the bladder and small intestines; and tears in the sutures that reconnect the remaining parts of the digestive system.

#### 11.2 Reporting Period

Adverse events will only be recorded for events that occur during or otherwise associated with the subject use of the mt-sDNA test (Cologuard), specifically the stool sample collection procedure. AEs are collected from the time of enrollment to return of the Stool Collection Kit. All AEs will be reported on the adverse event page(s) of the CRF.

#### 11.3 Serious Adverse Events

Serious adverse events are not expected for this study but will be reported to the Sponsor if they occur.

A serious adverse event (SAE) is any AE that results in one or more of the following outcomes.

- Death; Note: "Death" should not be reported as an SAE. The cause of death should be reported
  as the SAE. The only exception is "Sudden Death" when the cause is unknown.
- A life-threatening illness or injury;
- A permanent impairment of a body structure or a body function;
- Required in-patient hospitalization or prolongation of existing hospitalization;
- Necessitates medical or surgical intervention to prevent permanent impairment of a body structure or a body function; or
- Fetal distress, fetal death or a congenital abnormality or birth defect.

#### 11.4 Unanticipated Adverse Events

An unanticipated adverse device effect (UADE) is "any serious adverse effect on health or safety or any life-threatening problem or death caused by, or associated with, a device, if that effect, problem, or death was not previously identified in nature, severity, or degree of incidence in the investigational plan or application (including a supplementary plan or application), or any other unanticipated serious problem associated with a device that relates to the rights, safety, or welfare of subjects" (21 CFR 812.3(s)).

#### 11.5 Reporting Requirements

#### 11.5.1 SAE Reporting Requirements

If a SAE occurs, Exact Sciences or its designee is to be notified within 24 hours of awareness of the event by the Investigator. In particular, if the SAE is fatal or life-threatening, notification to Exact Sciences or its designee must be made immediately, irrespective of the extent of available adverse event information. This timeframe also applies to additional new information (follow-up) on previously forwarded SAE reports.

In the rare event that the Investigator does not become aware of the occurrence of a SAE immediately (e.g., if an outpatient study subject initially seeks treatment elsewhere), the Investigator is to report the

#### Master Clinical Protocol 2018-10

event within 24 hours after learning of it and document the time of his/her first awareness of the adverse event.

For all SAEs, the Investigator is obligated to pursue and provide information to Exact Sciences or its designee in accordance with the timeframes for reporting specified above. In addition, the Investigator may be requested by Exact Sciences or its designee to obtain specific additional follow-up information in an expedited fashion. This information may be more detailed than that captured on the adverse event case report form. In general, this will include a description of the adverse event in sufficient detail to allow for a complete medical assessment of the case and independent determination of possible causality. Information on other possible causes of the event, such as concomitant medications and illnesses must be provided. In the case of a subject death, a summary of available autopsy findings must be submitted as soon as possible to Exact Sciences or its designee. SAEs may be reported to the local IRB/EC per institutional requirements.

#### 11.5.2 Non-Serious Adverse Event Reporting Requirements

All AEs will be reported on the adverse event page(s) of the CRF. It should be noted that the form for collection of SAE information is not the same as the adverse event CRF.

#### 11.5.3 Reporting Requirements of Unanticipated Adverse Devices Effects (UADEs)

All UADEs must be reported by the Investigator to the Sponsor within 3 days from identification or awareness of the event. Investigators are responsible for preparing and submitting complete, accurate, and timely reports to the reviewing IRB/EC of any UADE occurring during an investigation as soon as possible, but in no event later than 10 working days after they first learn of the effect.

#### 11.5.4 Sponsor Reporting Requirements to Regulatory Authorities

Exact Sciences will immediately conduct an evaluation of any UADE. If Exact Sciences determines that an UADE presents an unreasonable risk to subjects Exact Sciences shall terminate all investigations or parts of investigations presenting that risk as soon as possible. Termination shall occur no later than 5 working days after the Sponsor makes this determination and not later than 15 working days after the Sponsor first received notice of the effect.

#### 12 DATA ANALYSIS AND STATISTICAL METHODS

Detailed methodology for summary and statistical analyses of the data collected in this study will be documented in a Statistical Analysis Plan. This document may modify the plans outlined in the protocol; however, any major modifications of the primary endpoint definition and/or its analysis will also be reflected in a protocol amendment.

#### 12.1 Effectiveness Endpoints

#### 12.1.1 Definitions

Advanced Neoplasia	Colonoscopic findings that include colorectal cancer (CRC) (category 1)
(AN)	and advanced adenoma (AA) (category 2).
Non-advanced neoplasia	Colonoscopic findings ≤ 1.0 cm that exclude colorectal cancer (CRC)
(NAN)	and advanced adenoma (AA) and include categories 3 – 5.
Sensitivity (Se)	The sensitivity (Se) or true positive fraction of the test is defined as

#### Master Clinical Protocol 2018-10

	TP/(TP + FN)
Specificity (Sp)	The specificity (Sp) or true negative fraction of the test is defined as TN/(TN+FP)
False positive fraction (FPF)	The false positive fraction (FPF) is defined as FP/(TN+FP)
Odds ratio	The odds ratio (OR) is defined as (TP/FP)/(FN/TN)
Negative likelihood ratio	The negative likelihood ratio (NLR) is defined as (1-Se)/(Sp)
Positive likelihood ratio	The positive likelihood ratio (PLR) is defined as Se/(1-Sp)
Negative Predictive	The Negative Predictive Value (NPV) is defined as: TN/(FN+TN) and/or
Value	[Sp*(1-Prevalence)]/[(1-Se)*(Prevalence+Sp*(1-Prevalence)].
Positive Predictive Value	The Positive Predictive Value (PPV) is defined as: TP/(TP+FP) and/or (Se*Prevalence)/[Se*Prevalence+(1-Sp)*(1-Prevalence)]

#### 12.2 Primary Endpoint

The primary endpoint of this study is the specificity of the mt-sDNA test (Cologuard) in the 45-49 age group in an average risk population, using colonoscopy with histopathology (when required) as the reference method. The primary analysis requires the one-sided 97.5% lower bound of the specificity of Cologuard to exceed 85.0%.

The primary endpoint of this study is to confirm the specificity of the mt-sDNA test (Cologuard) in the 45-49 age group in an average risk population. Specificity will be determined by comparing the mt-sDNA test result to the results of optical colonoscopic examination and confirmation of the colonoscopic findings by histopathology, if appropriate.

Possible categories of colonoscopic findings are as follows:

- 1. CRC, all stages (I-IV);
- 2. Advanced adenoma, including the following subcategories:
  - 2.1 Adenoma with carcinoma in situ or high-grade dysplasia, any size
  - 2.2 Adenoma, villous growth pattern (≥ 25%), any size
  - 2.3 Adenoma > 1.0 cm in size, or
  - 2.4 serrated lesion, > 1.0 cm in size;
- 3. 1 or 2 adenoma(s), > 5 mm in size, or < 10 mm/1.0 cm size, non-advanced;
- 4. > 3 adenomas, < 10 mm in size, non-advanced;
- 5. 1 or 2 adenoma(s), < 5 mm in size, non-advanced;
- 6. Negative no neoplastic findings, including the following subcategories:
  - 6.1 Negative, no colorectal neoplasia upon histopathological review
  - 6.2 No findings on colonoscopy, no biopsy(s) taken

Subjects with colonoscopic findings in categories 3-6 above will be included in the specificity analysis as negative outcomes for the primary endpoint calculation. Thus, specificity to advanced neoplasia (AN) will be calculated for the primary endpoint evaluation. The colonoscopically 'negative' population (category 6) will include those subjects with a colonoscopy showing no findings of colorectal neoplasia, non-neoplastic disease, and/or hyperplastic polyps  $\leq$  1 cm in diameter.

Subjects with no findings on the colonoscopy, no photographic evidence of cecal intubation and no documentation of cecal intubation in the report, will be deemed to be unevaluable and therefore will be excluded from all analyses. Subjects found to have occult inflammatory bowel disease (IBD) on

